Methods: Primary Aims

For total body weight loss (TBWL) as a continuous measure, we will use a two-sample t-test to examine the differences between the control and active treatment groups at each time period. We will also build one-sided confidence intervals to test whether the difference between groups exceeds a superiority margin of 5%. As a secondary analysis, we will also use a linear regression with TBWL as the dependent variable and group and other covariates of interest (gender, age, etc.) as independent variables. To assess any longitudinal effects, we will use a linear mixed effects model for weight over time, with fixed covariates for baseline weight, time, group, and a time / group interaction, and a random intercept to account for within-subject correlation. We will use a one-sided exact binomial test to determine if the response rate in the treatment group significantly exceeds 35%, with response defined by a loss of at least 5% of their body weight at the 12-month follow-up. We will also use Fisher's exact test to compare the response rates in each group, and, as a secondary analysis, will consider the use of a logistic regression to control for any other covariates of interest. To investigate possible longitudinal trends, we will fit a logistic mixed effects model, similar to the linear mixed effects model described above.

Methods: Secondary Aims

For each continuous and categorical variable at each time point, we will use a two-sample t-test and Fisher's exact test, respectively. Summary statistics (mean, standard deviation, quantiles, counts, and percentages) and plots will be produced for all demographic and study outcomes. We will investigate the effectiveness of the device by usage by including usage time as a continuous covariate in a linear model for TBWL. CTRI Biostatistics Core personnel will conduct all analyses using the latest version of R (R Foundation for Statistical Computing, Vienna, Austria. <http://www.R-project.org/>). No alpha spending function is applied to adjust for multiple comparisons across the secondary aims, and no claims will be made based on any of the secondary endpoints, which are instead viewed as hypothesis generating endpoints.

Missing Data

The primary hypotheses will be tested on the intent-to-treat population. A sensitivity analysis will be

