performed with the binary weight loss endpoint. This analysis will include a best-case scenario (assuming subjects with missing values have all lost over 5% body weight), a worst-case scenario (assuming no subjects with missing values have lost over 5% body weight), and a tipping point analysis (as described in Yan¹). We will check the assumption that the data is missing completely at random, and use multiple imputation techniques to reduce bias in the estimation of the treatment effect. Missing data will be clearly reported and included in tables.

Power Calculation

The primary outcomes are TBWL from the start of treatment until the 12-month mark and the number of subjects who lose at least 5% of their baseline total body weight. We will power both of these tests at the 0.025 significance level (a Bonferroni correction to maintain a family-wise error rate of 0.05 in our primary analysis). For TBWL, we will test the following null and alternative hypothesis:

$$\begin{aligned} H_0: \mu_t - \mu_c &\leq 5\% \\ H_1: \mu_t - \mu_c &> 5\% \end{aligned}$$

where μ_t and μ_c are the treatment and control mean TBWL in the ITT population. We will use a one-sided two-sample t-test to determine if there is a statistically significant difference in TBWL between our control and treatment arms beyond a superiority margin of 5%. With a total sample size of 90 subjects (30 sham and 60 active treatment), this t-test will have 80% power at the $\alpha = 0.025$ significance level to detect an effect size of $d = 0.63$. Assuming a similar standard deviation of TBWL as the ReShape trial (7.5%), this translates to a detectable difference in TBWL between the treatment and control groups of 4.75%. Assuming this same standard deviation, a two-sample superiority test will have 80% power assuming that the true difference between groups is 6.33%.

For the proportion of treatment subjects who lose at least 5% of their baseline total body weight, we will test the following null and alternative hypothesis:

$$\begin{aligned} H_0: P_t &\leq 35\% \\ H_1: P_t &> 35\% \end{aligned}$$

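### Plain Bonferroni on the two primary outcomes is valid but less efficient than Holm, which holds the same 0.05 and adds about 7 to 10 points of power to establish both

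*Combined protocol and SAP*

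**What the plan says.** All references are to Section 9, Statistical Considerations, unless noted.

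- **Outcomes (Power Calculation, opening sentence):** "The primary outcomes are TBWL from the start of treatment until the 12-month mark and the number of subjects who lose at least 5", the 5 being a percentage of baseline weight.
- **Error split (Power Calculation):** "We will power both of these tests at the 0.025 significance level (a Bonferroni correction to maintain a family-wise error rate of 0.05"). No step-down or other sequential procedure is named for the primary outcomes.
- **TBWL test (Power Calculation):** "We will use a one-sided two-sample t-test", with a null hypothesis that the group difference is at most 5%. Methods: Primary Aims also gives a two-sample t-test of the groups and one-sided confidence intervals for the 5% margin.
- **Responder test (Methods: Primary Aims):** "We will use a one-sided exact binomial test to determine if the response rate in the treatment group significantly exceeds 35", the 35 being a percentage.
- **Power (Power Calculation):** the numbers analysed are given in the words "With a total sample size of 90 subjects (30 sham and 60 active treatment"). The claim for the TBWL test, made for the 0.025 level, begins "this t-test will have 80% power at the"; the effect in question is stated as d = 0.63. It is converted to a 4.75% difference with an SD borrowed from another device trial: "Assuming a similar standard deviation of TBWL as the ReShape trial (7.5"%). A true difference of 6.33% is said to give 80% power for the margin test. The responder test is said to have 80% power at 0.025 for a 50.8% response.
- **Success rule:** neither Primary Outcome Measures nor Statistical Considerations says whether one outcome suffices or both are needed. No joint power is stated.

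**The concern.** Under plain Bonferroni the second outcome stays at 0.025 even after the first has been rejected. Holm then releases the full 0.05 to the remaining hypothesis, and the family-wise error rate is still at most 0.05 whatever the correlation between the tests. Every result that is significant under Bonferroni is significant under Holm, and some others are too.

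At stake is the chance of establishing both outcomes in a 90-subject trial. The error rate is not in question. The loss matters most for the responder test, whose exact power at 0.025 is already below the stated 80%.

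**Working it through.** **Inputs from the plan.** 60 active and 30 sham; SD 7.5%; TBWL difference 4.75% (zero null) or 6.33% (5% margin); responder null 35%, alternative 50.8%; one-sided 0.025 per test, 0.05 family-wise.

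**Assumptions.** TBWL is normal with equal SDs. The active mean is set so that 50.8% lose at least 5%: 5 + 7.5 × z(0.508) = 5.15%. The sham mean is 5.15% minus the difference under study. The plan gives no sham mean. It also gives no correlation between the two tests; these assumptions imply about 0.45.

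**1. Error split.** 0.025 + 0.025 = 0.05, as stated.

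**2. TBWL test alone.** SE = 7.5 × √(1/60 + 1/30) = 1.677. Noncentrality = 4.75 / 1.677 = 2.832 on 88 df. The critical value is 1.987 at 0.025 and 1.662 at 0.05. Power is 80.0% at 0.025 and 87.8% at 0.05. The plan's 80% reproduces for a zero null. Against the 5% margin, a true difference of 6.33% gives (6.33 − 5) / 1.677 = 0.793 and power of 12.0%. A true difference of 5 + 4.75 = 9.75% is needed for 80%.

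**3. Responder test alone (exact binomial, n = 60).** At 0.025, at least 29 responders are needed (exact level 0.0228) and power at 50.8% is 69.5%. At 0.05, at least 28 are needed (exact level 0.0412) and power is 77.9%. The stated 80% at 0.025 does not reproduce. The arcsine approximation with h = 0.321 gives 80.0% at 0.05 and 70.1% at 0.025.

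**4. Rules for rejecting both.** Let T1 and T2 be rejection of the TBWL null at 0.025 and 0.05, and R1 and R2 the same for response.
- Bonferroni: P(T1 and R1).
- Holm: P(T2 and R2, with T1 or R1) = P(T1 and R2) + P(T2 and R1) − P(T1 and R1).
- At least one rejected: P(T1 or R1) under both procedures, because Holm's first step is the Bonferroni test.

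**5. Hand check under independence (zero null, 4.75%).**
- Bonferroni: 0.7999 × 0.6954 = 0.556.
- Holm: 0.7999 × 0.7792 + 0.8781 × 0.6954 − 0.5563 = 0.678.

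**6. Patient-level simulation with the implied correlation (400,000 trials per row).**

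| TBWL null and true difference | Both, Bonferroni | Both, Holm | Both, each at 0.05 | At least one, either procedure |
|---|---|---|---|---|
| Zero, 4.75% | 60.5% | 70.8% | 71.7% | 89.0% |
| Zero, 5.11% (sham mean assumed 0.04%) | 63.4% | 73.1% | 73.8% | 91.4% |
| 5% margin, 6.33% | 11.1% | 18.0% | 18.4% | 70.5% |
| 5% margin, 9.75% | 60.7% | 70.9% | 71.8% | 89.0% |

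In the first row, TBWL alone goes from 80.0% to 84.1% and response from 69.5% to 75.6%. All of the gain in establishing both comes from these second-step rejections.

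**7. Sensitivity to correlation.** With a zero null, d = 0.63 and the exact binomial, both-outcome power under Bonferroni and then Holm is 55.3% and 67.5% at correlation 0, 63.8% and 72.9% at 0.7, and 67.5% and 75.1% at 0.9. The gain shrinks from about 12 to 8 points but persists.

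**The case against.** **Bonferroni is valid, pre-specified and simple.** This stands. It also yields simultaneous confidence bounds directly, which has some value here because Methods: Primary Aims assesses the 5% margin through one-sided intervals. A reader might infer that Bonferroni is never the better choice; this advantage is why that goes too far.

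**If both outcomes are required, 0.025 per test does buy error control.** A reader might infer that the split achieves nothing. Under a both-required rule, testing each at 0.05 already holds 0.05 for the joint claim, so no split is needed. Keeping 0.025 caps a false joint claim at 0.025 instead. The tests are one-sided and Specific Aims says that the data are to support regulatory submissions, so a sponsor may want the stricter level. Against that, the only overall level that the plan names is 0.05.

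**If one outcome is enough, trial-level success is unchanged.** This also stands: the last column of the table is the same under both procedures.

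**The gain depends on the TBWL hypothesis.** A reader might take 63% to 73% as the plan's chance of establishing both outcomes. It is not. That pair tests TBWL against zero and rests on a sham mean that the plan does not give. Against the stated 5% margin at 6.33%, the figures are 11% and 18%.

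**Correlation is not an argument for Holm.** The responder outcome is TBWL cut at 5%, so a reader might expect the overlap to drive the gain. The test statistics correlate at only about 0.45, Holm makes no use of correlation, and the gain falls as correlation rises.

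**Conclusion.** The point holds as a matter of efficiency. At the plan's own family-wise level of 0.05, Holm gives the same error control as the Bonferroni split and never rejects less. Power to establish both outcomes rises by about 10 points, from 61% to 71%, when TBWL is tested against zero at 4.75% or against the 5% margin at 9.75%. It rises by about 7 points, from 11% to 18%, against the margin at 6.33%. These figures assume normal TBWL, SD 7.5%, 60 and 30 analysed subjects and a 50.8% active response.

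The documents do not support reading this as a fault in error control. Two larger problems in the same paragraphs are separate, and Holm does not cure them: the margin test has about 12% power at 6.33%, and the exact binomial test has about 69.5%, each against a stated 80%.

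**What to change.** Replace the Bonferroni sentence in the Power Calculation with:

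*The two primary hypotheses are tested by the Holm procedure at family-wise one-sided 0.05: the smaller p-value against 0.025 and, if rejected, the other against 0.05.*

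State the success rule beside it. If both outcomes are required, say so, and say whether each is tested at 0.05 (enough to hold 0.05) or at 0.025 (a deliberate stricter choice).

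The cost is one sentence, with no extra subjects or data. The plan has double masking and no interim analysis, so the change can be made before unblinding. The drawback is that simultaneous bounds matching Holm are less simple than Bonferroni bounds; the text should therefore say how the one-sided interval for the 5% margin will be reported.

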9. RESEARCH DESIGN AND METHODS

Official Title A randomized, double blind sham controlled clinical trial to evaluate the efficacy of vestibular nerve stimulation (VeNS) (see Appendix 1), combined with a lifestyle modification program (see Appendix 2), compared to a sham control (see Appendix 1) and a lifestyle modification program as a means of reducing excess body weight.

Study Design

- Allocation: Randomized
- Endpoint classification: Efficacy Study
- Intervention Model: Parallel Assignment in 2:1 active to control allocation (Aim to recruit a total of 106 participants overall in the study across two sites, with a dropout allowance of 15% to generate a minimum of 60 active treatment and 30 control subjects). (In order to do this we estimate that we may have to screen up to 150 subjects). The UCSD site will aim to recruit a total of 60 subjects.
- Masking: Double Blind (Subject and all study staff including research dietitian, nursing and Outcomes Assessor)

Pre-screening of Subjects

In order to prevent subjects traveling in needlessly to the study site it is proposed that the study staff allow prospective subjects to pre-screen themselves over the phone. This will involve the study coordinator reading out the inclusion and exclusion criteria to prospective subjects during an initial phone call. The screening questionnaire will not be completed at this stage. Rather the purpose is to make prospective subjects aware as to what the inclusion and exclusion criteria are, since there is no point in them wasting their time and coming in if they are obviously ineligible.

This will also allow study coordinators to provide prospective subjects with a verbal description of the study to the subjects. The text that the coordinator will follow is included for review with this submission.

Overview of Clinical Study

Subject enrollments will be completed during Site Visit 1 (Baseline visit). The ACTRI site can

accommodate up to 3 enrollments per day. All subjects will be part of the study consisting of: Site Visit 1 (~5 hours, 0 months for enrollment); Site Visit 2 (~3.5 hours, 3-month time point); Site Visit 3 (~3.5 hours, 6 months); Site Visit 4 (final visit ~3.5 hours, 12 months); and Home Use Period (12 months).

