- The proportion of subjects who lose at least 5% of baseline truncal body fat in the active versus placebo treated groups. (As measured by a whole body DXA scan).
- The difference in mean percent loss of baseline visceral adipose tissue in the active versus placebo treated groups. (As measured by a whole body DXA scan).
- The proportion of subjects who lose at least 5% of baseline visceral adipose tissue in the active versus placebo treated groups. (As measured by a whole body DXA scan).

- Difference in lean muscle mass in the active versus placebo treated group. (As also automatically measured by the whole body DXA scan).
- Difference in bone mineral content in the active versus placebo treated group. (As also automatically measured by the whole body DXA scan).
- Blood pressure
- Heart rate
- Lipid profile (Assess total non-HDL cholesterol, and HDL to total cholesterol ratio)
- High-sensitivity C-reactive protein
- Oral glucose tolerance test (See Appendix 5)
- Fasting insulin level
- Waist and hip circumferences
- Body Mass Index (BMI)
- Adjustment of concomitant medication – both reduction and new medications
- Quality of life – IWQOL-Lite questionnaire. This validated instrument, developed by Duke University, has been used by a variety of researchers to assess various obesity treatment options and their impact on individual patients. The questionnaire is available in a number of languages including Spanish. A detailed description is available on this website: <https://olv.duke.edu/iwqol>. As can be seen on this website this instrument has been used extensively in studies relating to weight loss and obesity: <http://www.qualityoflifeconsulting.com/iwqol-litepublications.html>.
- Dose response analysis: it is likely that some subjects will not utilize their device for the mandated 5 hours per week. Usage data will be available from the devices as they can distinguish when they are genuinely being used as opposed to just being turned on with air between the electrodes. Data from such subjects will be analyzed in the main study but if possible a dose response analysis will also be carried out. Analysis will be in an intention to treat manner – see Statistical Considerations.

Safety Endpoints and Adverse Event Monitoring

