In response to a suggestion from the FDA that a second site be opened for the study, the sponsor is looking to open this second site at Queen's University Belfast. The proposal is that the second site for the study will be located at the [Northern Ireland Clinical Trials Unit, [name]](http://www.research.hscni.net/northern-ireland-clinical-trials-unit) (<http://www.research.hscni.net/northern-ireland-clinical-trials-unit>). UCSD will serve as the principal site for the study and the data from the Belfast site will be sent to UCSD for a final pooled analysis by the UCSD bio-statistics team at the CTRI.

The UCSD OCGA have been asked to establish an unfunded collaboration agreement with Queen's University. Part of this agreement will mandate that the Belfast ICF states explicitly that data collected will be shared with UCSD for analysis. In terms of this arrangement, the bio-statistics team at UCSD will be responsible for carrying out the final analysis of all the data. The study at the second site will be executed in accordance with GCP guidance and study monitoring will be in place throughout. The Research Plan as executed at UCSD will also be executed at the second site. Data for each of the primary, secondary and safety endpoints for each of the participants at the second site will be transferred electronically (with PHI removed) to [name] in bio-statistics at UCSD.

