Data will be transferred in an encrypted PDF format. Trial staff will be given direction on how to share the trial data and given access to one specific section of a controlled cloud service which is controlled via role based access. Once they have authenticated with the service and the service verifies that they have the correct role to access the system they will be directed to a single webpage within the application where they will be able to upload the encrypted PDF. This PDF is generated on the fly and is therefore not stored in another location that could become compromised. Generating the PDF on the fly means that the source data is extracted from the database, processed and delivered in the context of a single request. This is an important factor as this means that after the request finishes the data in the PDF will not be held in application memory once the request is finished and the data relating to the request is freed. After the PDF is generated it is delivered to the assigned statistician using TLS 1.2 (a strong protocol), ECDHE_ECDSA with X25519 (a strong key exchange), and AES_128_GCM (a strong cipher). These data will be transferred for each subject when they complete participation in the study. If they complete the study protocol this will be at the one-year mark, however, if they drop out early then data accrued up until that point will be sent.

References

STATISTICAL CONSIDERATIONS

These statistical considerations were constructed in conjunction with [name] of the bio-statistics unit at the ACTRI.

Randomization

Treatment assignments will be generated via a randomized block procedure, with block sizes randomly chosen in the set {2, 4, 6, 8, 10, 12}. Subjects will be assigned 2:1 between treatment and control groups. Stratification will be performed by gender and center.

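### The deciding weight-loss test and the t-tests on continuous secondary outcomes ignore the stratification factors, and center is named in no model; the tests stay valid but lose some precision.

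*Combined protocol and SAP*

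**What the plan says.** All of this is in Section 9 of the combined protocol and SAP unless stated otherwise.

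- **Randomization:** "Stratification will be performed by gender and center", with 2:1 allocation.
- **Study Design:** 106 subjects over two sites. "The UCSD site will aim to recruit a total of 60 subjects", which leaves 106 − 60 = 46 for the second site.
- **Data from the Belfast Site:** the second site's data "will be sent to UCSD for a final pooled analysis by the UCSD bio-statistics team at the CTRI".
- **Power Calculation:** "We will use a one-sided two-sample t-test to determine if there is a statistically significant difference in TBWL", with a null hypothesis that the difference is at most 5% and a significance level of 0.025.
- **Methods: Primary Aims:** besides the t-test at each time period, there is a secondary "linear regression with TBWL as the dependent variable and group and other covariates of interest (gender, age, etc.) as independent variables". For longitudinal effects there is a "linear mixed effects model for weight over time, with fixed covariates for baseline weight, time, group, and a time / group interaction", with a random intercept. A logistic regression with unnamed covariates may be considered for the 5% responder outcome.
- **Methods: Secondary Aims:** "For each continuous and categorical variable at each time point, we will use a two-sample t-test" (Fisher's exact test for the categorical ones). No claims are to rest on these endpoints.
- **Secondary Outcome Measures:** the DXA fat outcomes are percent losses from baseline. Others carry no scale, for example "Difference in lean muscle mass in the active versus placebo treated group". Section 6 speaks of changes from baseline for vital signs and, arguably, laboratory results.

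**The concern.** A trial that stratifies its randomisation by gender and center balances the arms on both. If either factor predicts weight loss, the difference in means becomes less variable. An unadjusted t-test does not see this: its standard error still contains the between-stratum variance, so the interval is wider than it need be and the test is conservative. Putting the strata and the baseline value into the model recovers that precision.

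The plan keeps adjustment out of the deciding test. Center, which here separates a US site from a UK site, is listed in no model. The open covariate list also means that the adjusted TBWL result could be shaped after the data are seen.

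For lean mass, bone mineral content, waist and hip circumference, BMI and IWQOL-Lite, the plan does not say whether visit values or changes are compared. The quantity estimated is therefore undefined, and the gain from using baseline could be small or large.

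What is at stake is interval width in a trial with only 30 evaluable controls. No false-positive risk arises.

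**Working it through.** **Inputs from the documents (Power Calculation):** SD of TBWL 7.5%; 60 active and 30 sham evaluable; one-sided 0.025; stated detectable effect d = 0.63, or 4.75%, at 80% power; 5% margin; a true difference of 6.33% quoted for the margin test.

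**Assumptions:** the documents give no variance explained (R²) and no baseline-to-follow-up correlations (r), so ranges are used for both.

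**Step 1: the plan's own figure.** By noncentral t with 88 df, d = 0.63 gives 79.6% power, and exactly 80% needs d = 0.6334. 0.6334 × 7.5 = 4.75 points. The stated figure reproduces.

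**Step 2: precision without adjustment.** SE = 7.5 × √(1/60 + 1/30) = 1.677. With t(0.975, 88) = 1.987, the 95% half-width is 1.987 × 1.677 = 3.33 points.

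**Step 3: precision with adjustment.** Adding gender, center and baseline weight leaves 90 − 5 = 85 df. Adjusted SE = 1.677 × √(1 − R²). The unadjusted sample size giving the same SE is 90/(1 − R²).

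| Assumed R² | SE | Ratio | Half-width | Power, 4.75 points beyond the null | Power at 6.33% against the 5% margin | Equivalent unadjusted N |
|---|---|---|---|---|---|---|
| none (t-test) | 1.677 | 1 | 3.33 | 80% | 12.0% | 90 |
| 0.01 | 1.669 | 0.995 | 3.32 | 80% | 12.1% | 91 |
| 0.05 | 1.635 | 0.975 | 3.25 | 82% | 12.4% | 95 |
| 0.10 | 1.591 | 0.949 | 3.16 | 84% | 12.9% | 100 |
| 0.20 | 1.500 | 0.894 | 2.98 | 88% | 13.9% | 112.5 |

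The first power column applies to a true difference of 4.75 against a null of zero, or equally 4.75 + 5 = 9.75 against the 5% margin. The second uses (6.33 − 5)/SD.

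**Step 4: conservatism of the t-test.** In a simulation, 106 subjects (60 and 46 by site) were randomised within gender-by-center strata with the listed block sizes and 15% random dropout. Some of those block sizes cannot be split exactly 2:1, so a randomised rounding rule was assumed. Only gender was made prognostic, with 50% or 70% female (assumption). There were 12,000 runs per setting. Two-sided size at a nominal 5%:

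| R² from gender | t-test, 50% female | t-test, 70% female |
|---|---|---|
| 0 | 4.9% | 5.2% |
| 0.05 | 4.4% | 4.8% |
| 0.10 | 4.3% | 4.3% |
| 0.20 | 3.5% | 3.3% |

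The model with gender and center had size 4.9% to 5.1% at R² of 0.05 to 0.20. The Monte Carlo error is √(0.05 × 0.95/12,000) = 0.2 points.

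A smaller simulation (4,000 runs, 90 evaluable subjects, four prognostic strata) gave power of 79.6% unadjusted against 79.3% adjusted at R² = 0, 81% against 84% at 0.10, and 82% against 87% at 0.20. At 4,000 runs its size estimates are noisier, so it is used here only for power.

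**Step 5: secondary outcomes.** Assume equal variances at baseline and follow-up, and an illustrative true effect of 0.3 SD. The ANCOVA SE relative to a change-score t-test is √((1 + r)/2); relative to a raw-value t-test it is √(1 − r²).

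| Assumed r | SE ratio vs change | Power, change to ANCOVA | SE ratio vs raw value | Power, raw to ANCOVA |
|---|---|---|---|---|
| 0.5 | 0.87 | 26% to 33% | 0.87 | 26% to 33% |
| 0.7 | 0.92 | 40% to 46% | 0.71 | 26% to 46% |
| 0.8 | 0.95 | 55% to 60% | 0.60 | 26% to 60% |
| 0.9 | 0.97 | 84% to 86% | 0.44 | 26% to 86% |

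**The case against.** The strongest reply is that nothing here is an error. A pre-specified unadjusted primary test with an adjusted supportive model is a legitimate choice. The plan already has a regression with gender and a mixed model with baseline weight, and its open wording would admit center. A late choice of covariates cannot alter the deciding test, because that test is fully specified.

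The gain may also be nothing. TBWL is already scaled to baseline weight, every R² is assumed, and at 1% to 5% the half-width moves only from 3.33 to between 3.32 and 3.25. Against the 5% margin at the plan's own 6.33%, power rises by 0.1 to about 2 points. Secondary endpoints support no claims, and the large gains there need raw visit values to be tested, which the plan does not say.

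Much of this stands. It fixes the weight of the point: efficiency and pre-specification, not validity. The size simulation also has limits. It needs a rounding rule that the plan does not give, it makes only gender prognostic, and at R² = 0.05 with 70% female its 4.8% cannot be told from 5%.

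None of this gives a reason to leave the strata out. If they and baseline weight predict nothing, the cost is three degrees of freedom. If they predict something, the interval narrows without another subject. Wording that merely permits center is not the same as specifying it.

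**Conclusion.** The concern holds as an efficiency point that should be acted on. The deciding TBWL test and the only test named for continuous secondary outcomes are unadjusted, randomisation is stratified by gender and center, and center is in no named model.

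For TBWL, if the covariates explain 5% to 10% of the variance, the gain is 2 to 4 points of power at 4.75 points beyond the null, or the equivalent of 5 to 10 evaluable subjects. At 20% it is 8 points and about 22 subjects; at 1% or less it is negligible. For secondary outcomes the gain is modest if changes are tested and large only if raw values are.

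These sizes rest on assumed R² and r, on the plan's SD of 7.5%, and on 60 versus 30 evaluable subjects. The low power against the 5% margin is a separate problem that adjustment does not solve: 12% at 6.33%, rising to 13% to 14% at R² of 10% to 20%.

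**What to change.** - Make the main analysis of 12-month percent TBWL a linear model with treatment, gender, center and baseline weight. Test the same one-sided 0.025 hypotheses, including the 5% margin, from the adjusted treatment difference and its interval.
- Replace the open covariate list in the secondary regression with that closed list.
- For every continuous secondary outcome, state the scale (visit value, change or percent change) and use ANCOVA with treatment, gender, center and the outcome's own baseline value.
- Keep the two-sample t-tests as supportive analyses.

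The cost is SAP wording only. Gender, center and the baseline values are already collected, no visit or measurement is added, and residual degrees of freedom fall from 88 to 85. The change should be made before unblinding; no interim analysis is planned.

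### The test of weight loss against a 5% margin is credited with 80% power at a true difference of 6.33%; on the plan's own inputs the power is about 12%

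*Combined protocol and SAP*

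**What the plan says.** Everything needed is in Section 9, Statistical Considerations, under Power Calculation. The null is that active minus sham mean TBWL is 5% or less; the alternative is that it exceeds 5%.

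- **Test:** "We will use a one-sided two-sample t-test to determine if there is a statistically significant difference in TBWL". The aim is a "statistically significant difference in TBWL between our control and treatment arms beyond a superiority margin of 5" percent.
- **Significance level:** "We will power both of these tests at the 0.025 significance level", which is a Bonferroni split of 0.05 over the two primary outcomes.
- **Sample size:** "With a total sample size of 90 subjects (30 sham and 60 active treatment").
- **SD:** "Assuming a similar standard deviation of TBWL as the ReShape trial (7.5" percent).

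Two power statements follow. The first gives 80% power at a standardised effect of 0.63, and says "this translates to a detectable difference in TBWL between the treatment and control groups of 4.75" percent. The second, directly after it, reads "Assuming this same standard deviation, a two-sample superiority test will have 80% power assuming that the true difference between groups is 6.33" percent. It changes neither the SD, the sample size nor the significance level.

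Methods: Primary Aims repeats the margin: "We will also build one-sided confidence intervals to test whether the difference between groups exceeds a superiority margin of 5" percent. Earlier in Section 9, Primary Outcome Measures words success differently: a difference in mean weight loss of at least 5% that is also statistically significant.

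**The concern.** The two power statements use the same SD, arms and level, yet they cannot both describe the hypothesis written above them. A detectable difference from a t-test is a distance from the null value. If 80% power needs a distance of 4.75 points and the null value is 5%, the true difference has to be 9.75%. The plan says 6.33%. Read as a total between-group difference, 4.75% is below the margin and so lies inside the null.

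This is the power statement for the first primary hypothesis of a study that Section 6 says is meant to support regulatory submissions. Anyone relying on it would expect to succeed four times in five at a true difference of 6.33%. The written test would fail about 88% of the time. A non-significant result could then be taken as evidence against the device when the test had little chance of succeeding. No interim analysis is planned, so no scheduled look would bring the problem to light.

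**Working it through.** **Inputs** (all from Power Calculation): margin 5 points; SD 7.5 points; 60 active and 30 sham; one-sided level 0.025.

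**Standard error and critical value.** SE = 7.5 × √(1/60 + 1/30) = 1.677 points. With 60 + 30 − 2 = 88 degrees of freedom, the one-sided 0.025 critical value is 1.987.

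**Reproducing the plan's first figure.** Using the noncentral t distribution, 80% power needs a standardised distance from the null of 0.633. Then 0.633 × 7.5 = 4.75 points, with power 80.0%. The figure reproduces as a distance from whatever null value is tested.

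**The second figure.** Distance from the stated null: 6.33 − 5 = 1.33 points, or 1.33 / 7.5 = 0.18 SD. Noncentrality: 1.33 / 1.677 = 0.793. Power = P(noncentral t on 88 df > 1.987) = **12.0%**. A normal approximation gives 12.2% and a simulation of 100,000 trials gives 12.0%.

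**Power of the written test at other true differences:**

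| True difference | Distance above margin | Power |
|---|---|---|
| 4.75% | −0.25 | 1.75% |
| 6.33% | 1.33 | 12.0% |
| 7.5% | 2.50 | 31% |
| 9.0% | 4.00 | 66% |
| 9.75% | 4.75 | 80% |

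**Observed difference needed to reject:** 5 + 1.987 × 1.677 = 8.33%.

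**What 80% power at 6.33% would take.** Either the SD falls to 1.33 / 0.633 = 2.1 points, or the 2:1 total rises to about 1,125. The first 2:1 total to reach 80% is 376 + 752 = 1,128 evaluable, or 1,128 / 0.85, about 1,328 recruited at the plan's 15% dropout.

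**Could another setting give 80% at 6.33%?** Each row changes one element and keeps SD 7.5%:

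| Variant | Power at 6.33% |
|---|---|
| Two-sided 0.025, margin 5% | 7.3% |
| One-sided 0.05, margin 5% | 19.5% |
| Two-sided 0.05, margin 5% | 12.3% |
| All 106 recruited (71/35), margin 5% | 13.4% |
| 45/45, margin 5% | 13.0% |
| One-sided 0.025, null of zero | 96.2% |

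None is near 80%.

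**Where 6.33 may come from (conjecture).** 5 + 0.842 × 7.5 × √(4/90) = 6.33. That would be the true difference at which the observed difference exceeds 5% in 80% of trials, with equal arms of 45 and no significance level. With the planned 60/30 split the same expression gives 5 + 0.842 × 1.677 = 6.41. Other routes also return 6.33, for example 4.75 / 0.75. The documents do not settle which was used, and the error does not depend on it.

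**The case against.** The strongest defence is that the sentence describes a different success rule. Primary Outcome Measures can be read as requiring an observed difference of at least 5% together with significance against zero. Significance against zero needs an observed difference of only 1.987 × 1.677 = 3.33%, so the 5% condition binds. At a true 6.33% the probability of meeting it is Φ(1.33 / 1.677) = 78.6%, close to the stated 80%. Methods: Primary Aims also lists an ordinary two-sample t-test first and adds the interval against the margin second. The sponsor may therefore have had this rule in mind.

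That does not rescue the sentence. Power Calculation writes the null as 5% or less and the level as 0.025. When the true difference is exactly 5%, the two-part rule succeeds half the time, so judged against the written null its error rate is about 50%. What stands is that the plan supports two success rules, with about 12% and 79% probability of success at the same true effect, and must say which governs.

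Three smaller points are fair. The 4.75% is correct as an excess over the margin; it fails only when read as the total difference, which is how it is worded. The plan never says that 6.33% is the expected effect, so the 88% failure rate applies if that is the true difference. The second primary outcome has its own calculation, which this error does not touch.

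**Conclusion.** The statement is wrong as written. For the hypothesis, test, level, arms and SD in Power Calculation, power at a true difference of 6.33% is 12.0% rather than 80%, and 80% is reached only at 9.75%. All inputs are the plan's own. The calculation also takes a common SD of 7.5% in both arms and 90 evaluable subjects; using all 106 recruited raises the figure only to 13.4%. Because it misstates the power of a primary hypothesis, it must be corrected.

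**What to change.** Replace the 6.33% sentence with wording such as:

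> For the null hypothesis of a difference of 5% or less, 60 active and 30 sham subjects with an SD of 7.5% give 80% power at a true difference of 9.75%; at a true difference of 6.33% the power is 12%.

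State beside it that 4.75% is the detectable difference when the null is zero, and that against the 5% margin it is the excess over the margin.

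If the sponsor means the rule in Primary Outcome Measures (significant against zero, with an observed difference of at least 5%), write that as the primary hypothesis in Power Calculation and Methods: Primary Aims, and quote its success probability: about 79% at a true 6.33%. Settle the choice before unblinding.

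Correcting the power statement is a change of protocol and SAP wording with no extra subjects. The price is a less favourable stated power. Adopting the two-part rule changes the primary hypothesis and, since the Progress Report shows enrolment under way, would need an amendment. Keeping both the 5%-margin test and 80% power at 6.33% would need over 1,100 evaluable subjects at the stated SD.
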